8.3 White blood Cell Growth Factors

If used, white blood cell growth factors, including biosimilars, must be used per ASCO guidelines (http://jco.ascopubs.org/content/24/19/3187.full) and NCCN Guidelines® Myeloid Growth Factors (http://www.nccn.org/professionals/physician_gls/pdf/myeloid_growth.pdf).

8.5 Adverse Event Reporting

Toxicities (including suspected reactions) that meet the expedited reporting criteria as outlined in Section 16.0 of the protocol must be reported to the Operations Office, Study Chair and NCI via CTEP-AERS, and to the IRB per local IRB requirements.

S1607 Page 58 Version Date 10/15/2021

STUDY CALENDAR	
	UDY CALENDA

9.0

	Post- Prog Off Treat											[
												-
	Pre- Prog Off Treat		×									
	At Prog		×			×		×				
86 f	18 18											
Cycle 6-36 ^f	17 17											
Cyc	16 16									×	×	
	15 K											
Cycle 5	84 14											
O	13 K		×⊲							×	×	
	12 2 ≤											
Cycle 4	×1											
	10 10							×		×	×	
3	≷o		×									ļ
Cycle 3	⊗ ⊗											
	\geq \sim									×	×	
2	0 ≦											
Cycle 2	5											
	≥4					×		×		×	×	
-	s ⊗											
Cycle 1	2 🔨							×				
0	> -									×	×	
_	Pre- Study		Х			Х	х	×				
		X-RAYS AND SCANS	Tumor Measurements (CT/MRI) ^d		SPECIMENS	Tissue biopsy ^e	Archival tissue ⁱ	Blood Specimen Submission (20 ml) ^e	TREATMENT	Talimogene laherparepvec (T-VEC)	Pembrolizumab (MK- 3475)	Click here for Footnotes.

NOTE: Forms are found on the protocol abstract page on the SWOG website (www.swog.org). Forms submission guidelines are found in Section 14.0.

outlined in NOTE: Unless indicated otherwise in the protocol, scheduled procedures and assessments (treatment administration, toxicity as sessment for continuous treatment, disease assessment, specimen collection, and follow-up activities) must follow the established SWOG guidelines as https://www.swog.org/sites/default/files/docs/2017-10/Best%20Practices%20upddate.pdf.

S1607 Page 59 Version Date 10/15/2021

Partial Control Con	
 FOOTN A Disection A Dise	

10.0 CRITERIA FOR EVALUATION AND ENDPOINT ANALYSIS

- 10.1 Measurability of Lesions
 - a. Measurable disease: Measurable disease is defined differently for lymph nodes compared with other disease and will be addressed in a separate section below.
 - Lesions that can be accurately measured in at least one dimension (longest diameter to be recorded) as ≥ 2.0 cm by chest x-ray, by ≥ 1.0 cm with CT or MRI scans, or ≥ 1.0 cm with calipers by clinical exam. All tumor measurements must be recorded in decimal fractions of centimeters (or millimeters).

The defined measurability of lesions on CT scan is based on the assumption that CT slice thickness is 0.5 cm or less. If CT scans have slice thickness greater than 0.5 cm, the minimum size for a measurable lesion should be twice the slice thickness.

- 2. Malignant lymph nodes are to be considered pathologically enlarged and measurable if it measures ≥ 1.5 cm in **SHORT AXIS** (greatest diameter perpendicular to the long axis of the lymph node) when assessed by scan (CT scan slice recommended being no greater than 0.5 cm).
- b. Non-measurable disease: All other lesions (or sites of disease), including small lesions (longest diameter < 1.0 cm or pathologic lymph nodes with ≥ 1.0 cm to < 1.5 cm short axis), are considered non-measurable disease. Bone lesions, leptomeningeal disease, ascites, pleural/pericardial effusions, lymphangitis cutis/pulmonitis, inflammatory breast disease, and abdominal masses (not followed by CT or MRI), are considered non-measurable as are previously radiated lesions that have not progressed

- c. Notes on measurability
 - 1. For CT and MRIs, the same type of scanner should be used and the image acquisition protocol should be followed as closely as possible to prior scans. Body scans should by performed with breath-hold scanning techniques, if possible.
 - 2. PET-CT: At present, the low dose or attenuation correction CT portion of a PET-CT is not always of optimal diagnostic CT quality for use with RECIST measurements. However, if the site can document that the CT performed as part of a PET-CT is of identical diagnostic quality to a diagnostic CT, then the CT portion of the PET-CT can be used for RECIST measurements and can be used interchangeably with conventional CT.
 - 3. Ultrasound: Ultrasound is not useful in assessment of lesion size and should not be used as a method of measurement.
 - 4. Cystic lesions that meet the criteria for radiographically defined simple cysts should not be considered as malignant lesions (neither measurable nor non-measurable) since they are, by definition simple cysts.
 - 5. If a target lesion becomes very small some radiologists indicate that it is too small to measure. If the lesion is actually still present, a default measurement of 0.5 cm should be applied. If the radiologist believes the lesion has gone, a default measurement of 0.0cm should be recorded.

10.2 Objective Status at Each Disease Evaluation

Objective Status is to be recorded at each evaluation. All measurable lesions up to a maximum of 2 lesions per organ 5 lesions in total, representative of all involved organs, should be identified as target lesions at baseline. All other lesions (or sites of disease) including any measurable lesions over and above the 5 target lesions should be identified as non-target lesions. Measurements must be provided for target measurable lesions, while presence or absence must be noted for non-target measurable and non-measurable disease.

For studies that use disease progression as an endpoint, whole body scanning at specific intervals is necessary to determine that progression is NOT present outside of the "target" areas. Therefore, in these studies it is not acceptable to image only the "target" areas of the body in follow-up scans. For study-specific imaging requirements, see the Study Calendar in Section 9.0.

- a. Complete Response (CR): Complete disappearance of all target and non-target lesions (with the exception of lymph nodes mentioned below). No new lesions. No disease related symptoms. Any lymph nodes (whether target or non-target) must have reduction in short axis to < 1.0 cm. All disease must be assessed using the same technique as baseline.
- b. **Partial Response (PR)**: Applies only to patients with at least one measurable lesion. Greater than or equal to 30% decrease under baseline of the sum of appropriate diameters of all target measurable lesions. No unequivocal progression of non-measurable disease. No new lesions. All target measurable lesions must be assessed using the same techniques as baseline.
- c. **Stable**: Does not qualify for CR, PR, Progression or Symptomatic Deterioration. All target measurable lesions must be assessed using the same techniques as baseline.
- d. **Progression**: One or more of the following must occur: 20% increase in the sum of appropriate diameters of target measurable lesions over smallest sum observed (over baseline if no decrease during therapy) using the same techniques as baseline, as well as an absolute increase of at least 0.5 cm. Unequivocal progression of non-measurable disease in the opinion of the treating physician (an explanation must be provided). Appearance of any new lesion/site. Death due to disease without prior documentation of progression and without symptomatic deterioration (see Section 10.2e).

NOTE: Any initial documentation of progression at the Week 9 assessment (or earlier) must be confirmed by a second determination of progression at the Week 13 assessment. If the Week 13 assessment documents an absence of progression, the patient's disease is assumed not to have progressed. If the Week 13 assessment is inadequate and there are no subsequent assessments documenting absence of progression, the initial documentation of progression will be considered definitive. After the disease assessment at Week 13, the documentation of any of the criteria in the paragraph above will be counted as disease progression.

Notes regarding new lesions: FDG-PET imaging can complement regular scans in identifying new lesions according to the following algorithm.

1. Negative FDG-PET at baseline, with a positive FDG-PET at follow-up is a sign of progression based on a new lesion.

- 2. No FDG-PET at baseline and a positive FDG-PET at follow-up corresponding to a potential new site of disease must have a confirmation by anatomical assessment (e.g., CT, MRI, x-ray) as new site of disease to be considered progressive disease. In such a case, the date of progressive disease will be the date of the initial abnormal FDG-PET.
- e. **Symptomatic deterioration:** Global deterioration of health status requiring discontinuation of treatment without objective evidence of progression. Efforts should be made to obtain objective evidence of progression after discontinuation.
- f. **Assessment inadequate, objective status unknown.** Progression or symptomatic deterioration has not been documented, and one or more target measurable lesions have not been assessed or inconsistent assessment methods were used.
- g. Objective status notes:
 - 1. Non-measurable and non-target measurable disease do not affect Objective Status in determination of CR (must be absent--a patient who otherwise has a CR, but who has non-measurable or non-target measurable disease present or not assessed, will be classified as having a PR). However, non-measurable and non-target lesions are included in determination of progression (if new sites of disease develop or if unequivocal progression occurs in the opinion of the treating physician).
 - 2. An objective status of PR or stable cannot follow one of CR. Stable can follow PR only in the rare case that tumor increases too little to qualify as progression, but enough that a previously documented 30% decrease no longer holds.
 - 3. In cases for which initial flare reaction is possible (hypercalcemia, increased bone pain, erythema of skin lesions), objective status is not progression unless either symptoms persist beyond 4 weeks or there is additional evidence of progression.
 - 4. Lesions that appear to increase in size due to presence of necrotic tissue will not be considered to have progressed.
 - 5. For bone disease documented on bone scan only, increased uptake does not constitute unequivocal progression. However, increase in the soft tissue component of a lesion as measured by CT or MRI would constitute progression.
 - 6. Appearance of new pleural effusions does not constitute unequivocal progression unless cytologically proven of neoplastic origin, since some effusions are a toxicity related to therapy or other medical conditions. Increase in the size of an existing effusion does not constitute unequivocal progression, since the fluid status of the patient could alter the size of the effusion.
 - 7. If CR determination depends on a lesion for which the status is unclear by the required tests, it is recommended the residual lesion be investigated with biopsy or fine needle aspirate.

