7.3 Prohibited and Cautionary Concomitant Medications

Patients should not receive the following therapies during this trial:

- Antineoplastic systemic chemotherapy or biological therapy.
- Immunotherapy not specified in this protocol.
- Any non-study anti-cancer agent (investigational or non-investigational).
- Investigational agents other than pembrolizumab (MK-3475) and talimogene laherparepvec (T-VEC).
- Radiation therapy
 - Note: Administration of palliative radiation therapy to non-targeted lesions is allowed.
- Anti-viral agents, unless approved after consultation with the study chairs.
- Live vaccines: Examples of live vaccines include, but are not limited to, the following: measles, mumps, rubella, chicken pox, shingles, yellow fever, rabies, Bacillus Calmette-Guérin (BCG), and typhoid (oral) vaccine. Seasonal influenza vaccines for injection are generally killed virus vaccines and are allowed; however, intranasal influenza vaccines (e.g. Flu-Mist®) are live attenuated vaccines, and are not allowed.
- Systemic glucocorticoids for any purpose other than to modulate symptoms from an event of suspected immunologic etiology. The use of physiologic doses of corticosteroids may be approved after consultation with the Study Chairs.

Patients who, in the assessment by the investigator, require the use of any of the aforementioned treatments for clinical management should be removed from protocol treatment. Patients may receive other medications that the investigator deems to be medically necessary.

Any steroid use other than emergency situations must be discussed with the study chair.

- 7.4 Criteria for Removal from Protocol Treatment
 - a. Completion of protocol treatment (36 cycles)
 - b. Progression of disease or symptomatic deterioration (as defined in Section 10.2).
 - 1. A minority of subjects treated with immunotherapy may derive clinical benefit either delayed responses, stable disease, or increased overall survival despite initial evidence of progressive disease (PD).

Patients may be permitted to continue treatment beyond initial RECIST 1.1-defined PD as long as they meet the following criteria:

- Patients must be clinically stable with no change in performance status due to disease progression.
- No indication for immediate alternative treatment.

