10.5 Progression-Free Survival

From date of registration to date of first documentation of progression (see note in Section 10.2d), or death due to any cause. Patients last known to be alive without report of progression are censored at date of last contact.

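### The Week 13 confirmation rule lets an assessment made after non-protocol therapy overturn an early progression, which can bias the secondary PFS estimates upward

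*Combined protocol and SAP*

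**What the plan says.** The note under Section 10.2d says that progression at Week 9 or earlier "must be confirmed by a second determination of progression at the Week 13 assessment". It then gives two ways in which the early progression can fall:

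- "If the Week 13 assessment documents an absence of progression", the patient is treated as not having progressed.
- If Week 13 is inadequate, the early progression stands only when "there are no subsequent assessments documenting absence of progression, the initial documentation of progression will be considered definitive". A later assessment without progression therefore also overturns it.

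Section 10.5 defines PFS as running "From date of registration to date of first documentation of progression", with a pointer to this note, or to death from any cause. Its only censoring rule is this: "Patients last known to be alive without report of progression are censored at date of last contact". Neither section mentions non-protocol anticancer therapy.

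Three other sections bear on the point:

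- **Section 7.4b** allows treatment beyond a first progression only under conditions, one of which is "No indication for immediate alternative treatment".
- **Section 7.3** takes patients who need other anticancer treatment off protocol treatment, but allows palliative radiation to lesions that are not targets. Section 5.2e lets palliative radiation or surgery be considered for symptomatic non-target lesions.
- **Section 10.3** limits best response to the time on protocol treatment.

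**The concern.** Waiting for confirmation makes sense for pseudoprogression under continued study treatment: if the lesions settle without other treatment, the early reading was misleading. That reasoning fails once something else has been given. An absence of progression at Week 13 may then reflect the new systemic agent, the radiation or the surgery.

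The patients most exposed to this include those whose first progression was clear enough to call for other treatment at once. Read literally, the note can turn such a failure into a progression-free patient. PFS then continues to a later progression, to death, or to censoring at last contact. The median PFS and the PFS rate at a fixed time would partly describe the next therapy.

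**Working it through.** **1. Does any text close the gap?**

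| Place | Limits which assessments count? |
|---|---|
| 10.2d note | No condition on treatment status or intervening therapy |
| 10.5 PFS | No event or censoring rule at the start of other therapy |
| 7.4b | Dates progression from the first assessment meeting 10.2d, which includes the note, so it does not settle the matter |
| 10.3 best response | Yes: time on protocol treatment |
| 14.4f Late Effects Form | Yes: before non-protocol treatment |

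The protocol draws this line for best response and late toxicity, but not for PFS.

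**2. How it can happen.**

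- *Off protocol treatment.* The patient progresses at Week 9, stops study drugs and starts another systemic therapy. Follow-up continues under Section 7.6. If an assessment at Week 13 shows no progression, the note sets the Week 9 event aside.
- *On protocol treatment.* Unequivocal progression of a non-target lesion counts as progression. That lesion may be given palliative radiation under Section 7.3, and the Week 13 assessment may then read as not progressed.

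**3. Direction.** Compared with keeping the initial date, overturning it replaces an event at or before Week 9 with a later event or with censoring at a later contact. No patient's PFS becomes shorter, so the bias has one sign.

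**4. The plan's own precision.** Section 11 gives the 95% half-width for a PFS rate as 23.7% (Cohort A, 17 eligible) and 19.6% (Cohort B, 25 eligible).

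- 1.96 × √(0.25/17) = 0.2377, which agrees with 23.7% up to truncation.
- 1.96 × √(0.25/25) = 0.1960, which agrees.

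**5. Effect per patient on the 6-month rate**, assuming no censoring before 6 months and that each reclassified patient remains event-free to 6 months (k = number of patients reclassified):

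| k | Cohort A, k/17 | Cohort B, k/25 |
|---|---|---|
| 1 | 5.9 points | 4.0 points |
| 2 | 11.8 | 8.0 |
| 3 | 17.6 | 12.0 |
| 4 | 23.5 | 16.0 |

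**6. Effect on the median: an illustration on assumed data.** Suppose all events fall on scan weeks 9, 13, 25 and 37. In Cohort A assume 9, 2, 3 and 3 events at those weeks; in Cohort B, 13, 3, 5 and 4. The median is the 9th ordered time of 17, or the 13th of 25, and is Week 9 in both. Move k of the Week 9 events to Week 37:

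- k = 1 puts the median at Week 13 in both cohorts.
- k = 3 (Cohort A) or k = 4 (Cohort B) puts it at Week 25.

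The example was chosen with just over half progressing at Week 9, where the median is most sensitive. It shows what is possible and is not a forecast.

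**7. Primary design.** Exact two-stage binomial calculation gives:

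- Cohort A (continue on at least 1/9, succeed on at least 2/17): alpha 0.172, power 0.902. The plan states 17.2% and 90.2%.
- Cohort B (continue on at least 2/16, succeed on at least 5/25): alpha 0.095, power 0.903. The plan states 10% and 90%.

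These rest on confirmed response, so a change to the PFS rule alters none of them.

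**The case against.** The case against has real force, and most of it narrows the point.

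- **Any later scan erases an early progression.** A reader might infer this, but a later assessment matters only if Week 13 is inadequate. Once Week 13 confirms progression, nothing reverses it.
- **The protocol instructs that post-switch scans count.** It does not. The fault is an omission: the rule is stated without the condition it needs.
- **Best response and the go/no-go decision are compromised.** Section 10.3 stops a scan taken after protocol treatment has ended from improving best response, and the decision rules use confirmed response. The protection is large but not complete, because a patient given local therapy to a non-target lesion may still be on protocol treatment.
- **Perhaps no such scans are collected.** The study calendar has separate off-treatment columns before and after progression, but it is broken in the available text and its footnotes are unreadable. What is required after an unconfirmed early progression off treatment cannot be settled. The on-treatment route does not depend on this.
- **Surgery may not clear the progression.** Under Section 10.2f an assessment is inadequate if a target lesion was not assessed, so removal of a target lesion could leave the early progression standing. That does not cover non-target lesions.
- **PFS is secondary and only estimated, with wide intervals.** True. But those half-widths describe random error; they do not allow for a bias that always runs one way.

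A reader might also put a total size on the bias. If 30% to 50% of patients progressed at Week 9 and 10% to 20% of those were overturned after other therapy, 3% to 10% of all patients would be affected (0.30 × 0.10 to 0.50 × 0.20). The documents support neither range. The product is also a ceiling for the 6-month rate, since progression after Week 13 counts at once and death always counts.

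**Conclusion.** The point holds as a gap in the PFS definition. As written, Sections 10.2d and 10.5 allow an assessment made after non-protocol systemic therapy, or after local treatment of the progressing non-target lesion, to overturn a progression documented at Week 9 or earlier. The effect on PFS can only be upward.

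Its size is 5.9 points (Cohort A) or 4.0 points (Cohort B) on the 6-month rate for each such patient who stays event-free to 6 months without earlier censoring. The median can move by a scan interval or more if it lies near the early assessments. The number of patients affected cannot be derived from the documents and may be zero.

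The sample sizes, alpha and power are unaffected, and the primary response-rate decision is largely protected. This is a correction worth making to a secondary endpoint, not a threat to the trial's main conclusion.

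**What to change.** Add to the note in Section 10.2d, in these or similar words:

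> For the PFS analysis, only assessments made before any non-protocol systemic anticancer therapy, or before radiation or surgery to the lesion that defined the progression, can overturn an initial progression. Otherwise the date of the initial progression is the PFS event date.

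State in the same place whether a missed Week 13 assessment counts as inadequate. Report PFS under the current rule as a sensitivity analysis.

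The cost is small. The start date of other systemic therapy, and the date and site of any local therapy, are needed only for patients with progression at Week 9 or earlier. Reported PFS may be slightly shorter. A rare true pseudoprogression that received local therapy would count as an event, even in a patient still on study drugs; the sensitivity analysis would show how much this matters. The change governs endpoint classification only and alters no patient's treatment.

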10.3 Best Response

This is calculated from the sequence of objective statuses. Best response should be documented for as long as the patient remains on protocol treatment.

- a. CR: Two or more consecutive objective statuses of CR a minimum of four weeks apart.
- b. PR: Two or more consecutive objective statuses of PR or better a minimum of four weeks apart but not qualifying as CR.
- c. Unconfirmed CR: One objective status of CR but not qualifying as CR or PR.
- d. Unconfirmed PR: One objective status of PR but not qualifying as CR, PR or unconfirmed CR.
- e. Stable/no response: At least one objective status of stable/no response documented at least 6 weeks after registration, but not qualifying as anything else above.
- f. Increasing disease: Objective status of progression within 13 weeks of registration, not qualifying as anything else above.
- g. Symptomatic deterioration: Objective status of symptomatic deterioration within 13 weeks of registration, not qualifying as anything else above.

Inadequate assessment, response unknown: Progression or symptomatic deterioration greater than 13 weeks after registration and no other response category applies.

